PROTOCOL AMENDMENT #4

LCCC 1930: Quantitative PET-MRI Imaging Correlated with Transcriptome Analysis for Noninvasive Characterization of Renal Cell Carcinomas

AMENDMENT INCORPORATES (check all that apply):

- Editorial, administrative changes
- Scientific changes
- Therapy changes
- Eligibility Changes

AMENDMENT RATIONALE AND SUMMARY:

The changes included in this amendment represent a better understanding of the patient population and clinical practices of UNC providers. Numerous patients have been evaluated since the beginning of the trial who have a primary renal mass smaller than 7 cm but with clear evidence of advanced disease. Additionally, as it is standard of care for patients with distant disease to receive a cytoreductive nephrectomy, inclusion of patients from this sub-set of the population could strengthen our understanding of the heterogeneity of clearly more aggressive ccRCC tumors.

List of updates to the protocol:

1. The radiological evaluation of tumor size was changed from ≥ 7 cm to ≥ 4 cm as inclusion criteria in the following sections: 1.3 and 3.1.3.
2. The number of samples to be collected was changed in section 1.1 to correspond with the study design as described in section 7.1.
3. The exclusion criterion 3.2.7 "Evidence of distant disease on physical exam or initial imaging" has been removed. It is standard practice for patients with distant ccRCC to undergo a cytoreductive nephrectomy and inclusion of these patients could further inform risk-stratification of patients with ccRCC.
4. The tumor size listed in 7.1 was changed from ≥ 7 cm to ≥ 4 cm.
5. The exclusion criterion 3.2.1 was updated to clarify patients suffering from claustrophobia severe enough to require sedation will be excluded from the study.

PROTOCOL AMENDMENT #3

LCCC 1930: Quantitative PET-MRI Imaging Correlated with Transcriptome Analysis for Noninvasive Characterization of Renal Cell Carcinomas

AMENDMENT INCORPORATES (check all that apply):

- Editorial, administrative changes
- Scientific changes
- Therapy changes
- Eligibility Changes

AMENDMENT RATIONALE AND SUMMARY:

The size and BMI criteria are unnecessary for the successful execution of the protocol and have led to the exclusion of many potential candidates who otherwise may have been good study subjects.

List of updates to the protocol:

1. Removed size restrictions from section 3.1 Inclusion Criteria.
2. Removed BMI limit from section 3.2 Exclusion Criteria.

***THE ATTACHED VERSION DATED April 21, 2021 INCORPORATES THE ABOVE REVISIONS
ATTACH TO THE FRONT OF EVERY COPY OF PROTOCOL***

PROTOCOL AMENDMENT #2

LCCC 1930: Quantitative PET-MRI Imaging Correlated with Transcriptome Analysis for Noninvasive Characterization of Renal Cell Carcinomas

AMENDMENT INCORPORATES (check all that apply):

- Editorial, administrative changes
- Scientific changes
- Therapy changes
- Eligibility Changes

AMENDMENT RATIONALE AND SUMMARY:

Clarification of study procedures drives the changes of this amendment. The Lineberger Comprehensive Cancer Center (LCCC) Office of Clinical and Translational Research (OCTR) is now supporting portions of this work. Many of the changes in language in this amendment accommodate the standard procedures for OCTR.

List of updates to protocol:

1. OCTR compliance statement added to section 1.4
2. Secondary objective moved to exploratory section
3. Eligibility criteria 3.1.2 modified to incorporate signing of both adult consent and HIPAA authorization
4. Eligibility criteria 3.1.4 modified to indicate surgery is standard of care, and not planned per research protocol
5. Eligibility criteria 3.1.7 modified to indicate nephrectomies must be done in Chapel Hill, as there is currently no mechanisms to collect multifocal tissue from other institutions.
6. Eligibility criteria 3.1.9 regarding pregnancy tests modified to match IRB application. This modification requires pregnancy testing on the day of imaging, rather than within 7 days prior to imaging.
7. Exclusion criteria 3.2.1 added the need for lorazepam to tolerate MRI.
8. Exclusion criteria 3.2.2 edited for clarification that gadolinium contrast hypersensitivity should be documented
9. Exclusion criteria 3.2.8 and 3.2.11 edited to use standard OCTR language
10. Study schema 4.1 edited for clarity, schema and study plan has not changed
11. Section 4.2 regarding patient identification and consent updated to include standard language
12. Section 4.4 edited to clarify that dosing is measured and recorded, but cannot be controlled precisely.
13. The time and events table in section 5.0 updated for clarity, time and events have not changed.
14. Section 7.4 Data management was updated to describe how patient information would be maintained
15. Sections 8.2, 8.3, 8.4, 8.5.2 were updated to standard contain language for standard OCTR and Lineberger procedures

LINEBERGER COMPREHENSIVE CANCER CENTER
CLINICAL ONCOLOGY RESEARCH PROGRAM

1.0 BACKGROUND AND RATIONALE

1.1 Study Synopsis

The objective of this study is to evaluate the utility of simultaneous positron emission tomography (PET) and magnetic resonance imaging (MRI) in characterizing the molecular subtypes of clear cell renal cell carcinomas (ccRCC) to potentially inform prognosis and treatment decisions. Previous results on a small number of subjects at UNC demonstrated a relationship between PET-MRI imaging characteristics and tumor subtype composition as determined by transcriptome analysis of surgical core samples in ccRCC. ccRCC has been classified into two molecular subtypes, ccA and ccB, on the basis of expression of a group of 34 genes; the two subtypes have been shown to have clear differences in prognosis. These tumors are notoriously heterogeneous; a single tumor can contain both subtypes, and full tumor molecular characterization is infeasible. Imaging, however, offers a snapshot of the whole tumor. If imaging characteristics prove to be predictive of subtype composition, early prognostic information would be available and different approaches to treatment may be enabled.

In this project, we will image 17 ccRCC subjects on simultaneous PET-MRI and quantify the metabolically-active fraction of the tumor from images. Up to ten core samples will be taken from each tumor post-surgery and classified as ccA or ccB subtype using transcriptome analysis. The imaging-based measures will be correlated with the fraction of tumor cores classified as ccB. We hypothesize that the metabolically-active tumor volume fraction derived from simultaneous PET-MRI imaging is correlated with the fraction of tumor cores classified as ccB subtype from transcriptome analysis.

This study is designed to provide preliminary information on the relationship between imaging metrics and tumor subtype composition in 17 ccRCC subjects. The primary objective is to evaluate the capabilities of MRI/PET in prediction of ccB burden.

Information from this study may be used to estimate effect size for power calculation and sample size considerations for possible future studies in the use of combined PET-MR to be used for prognostic information in ccRCC cases and potentially to enable risk-stratification that is not currently possible.

1.2 Background

Simultaneous PET/MR imaging [1]–[7] offers exciting opportunities to visualize and quantify soft-tissue tumors [2]. MRI offers superb soft-tissue contrast for anatomical information as well as a flexible suite of other techniques providing functional and physiological information. PET offers sensitive molecular imaging via radioactive tracers and is widely used for assessment of tumor glucose metabolism. Together, the two modalities provide complementary, synergistic information. Because of MRI's superior soft-tissue contrast, it is considered a much better anatomical guide

for PET quantitative analyses for tumors in soft tissue regions as compared to standard-of-care PET-CT. Simultaneous PET-MR also provides inherently-aligned PET and MR, efficient simultaneous acquisition, and the opportunity for new approaches to PET quantitative analysis guided by detailed MR images.

Nonmetastatic clear cell renal cell carcinomas are generally treated with nephrectomy, although research has subclassified them into two [8] or as many as four [9] subtypes based on gene expression; the subtypes have been shown to have differing prognoses and progression [8]–[11]. We focus primarily on the two subtypes ccA and ccB [8] and ask whether these two exhibit distinct PET-MRI imaging characteristics that can be used to subtype them noninvasively. An eight-subject pilot study conducted on PET-MRI at UNC demonstrated that quantitative PET-MRI imaging, using nonstandard measures incorporating the entire tumor, was strongly correlated with presence or absence of ccB patterns in the tumors [12]. Transcriptome analysis results from the study justified the import of PET in noting that many of the upregulated genes associated with ccB were involved in glucose transport and metabolism, the mediators of 18-FDG uptake. Thus, there is a strong biologic rationale as to why PET-MRI could predict ccB burden, but the small number of subjects in that study limits confidence. Also, the fact that these tumors are highly heterogeneous suggests that imaging alone provides an opportunity for early characterization of ccB burden across the entire tumor where gene expression profiling would be invasive and costly. Also, with the excellent soft-tissue contrast of MRI, the system has the potential for greater anatomical detail to guide interpretation of FDG activity. UNC has one of the few PET-MR scanners in the country, making it one of few centers in the US capable of conducting this study.

1.3 Purpose and Rationale

This is a prospective study of the use of combined PET-MR [1-7] for prediction of tumor subtype composition in ccRCC. Additional data analysis using the prior study from UNC suggests a strong correlation between the fraction of the tumor exhibiting moderate to high FDG uptake and the number of cores found to be ccB type. These results guide the hypothesis of this study: the metabolically-active tumor volume fraction derived from simultaneous PET-MRI imaging of clear-cell renal cell carcinomas is correlated with the fraction of tumor cores classified as ccB subtype from transcriptome analysis. If so, in the future, application of PET-MRI may offer prognostic information and opportunities for risk stratification.

We propose that the results of a single PET-MRI study prior to surgery will predict ccA/ccB content of the tumor. Patients will have clinically-suspected ccRCC based on prior imaging, with tumor size $\geq 4\text{cm}$. Subjects must have a planned nephrectomy schedule that will allow PET-MRI imaging within 4 weeks prior to surgery. Once patient identification occurs, the patient will be assessed for the study via the inclusion and exclusion criteria. Among other criteria, patients must have no contraindications against 18F-FDG PET nor MRI with gadolinium contrast. After recruitment by the study coordinator and informed consent, the patient will be admitted to the study and scheduled for imaging.

Patients in our study will receive their PET/MRI scan on the Biograph mMR combined PET-MRI scanner at the Biomedical Research Imaging Center. The PET-MRI scans will be evaluated retrospectively and will not be used in the determination of treatment.

Quantitative measures from PET and MRI will be computed: Quantitative measures from PET will be computed, including tumor maximum SUV, tumor mean SUV, and fraction of tumor volume over threshold SUV 2.0 (FTVOT2), as well as Metabolic Tumor Volume (MTV) and Total Lesion Glycolysis (TLG).

Quantitative measures from MRI will be computed including tumor volume, apparent diffusion coefficient, dynamic contrast enhancement, and tumor water content. All quantitative measures will be compiled into a complete image-based characterization of each tumor.

Patients will undergo nephrectomy within 4 weeks of imaging. Up to ten samples will be taken from each tumor, spatially distributed, and stored according the lab manual. Non-ccRCC histologies will be excluded from further analysis. RNA will be extracted and each sample will be classified as ccA or ccB using the ClearCode34 Nanostring classifier as previously described using a 34-gene custom Nanostring probe (NanoString Technologies, Seattle, WA).[13] Each sample will then be categorized as ccB or ccA or equivocal. The fraction of samples classified as ccB will be used in further analysis.

1.4 Compliance Statement

This study will be conducted in full accordance to all applicable University of North Carolina (UNC) Research Policies and Procedures and all applicable Federal and state laws and regulations including 45 CFR 46, and the Health Insurance Portability and Accountability Act (HIPAA) Privacy Rule. Any episode of non-compliance will be documented.

The investigators will perform the study in accordance with this protocol, will obtain consent, and will report unexpected problems in accordance with The UNC IRB Policies and Procedures and all federal requirements. Collection, recording, and reporting of data will be accurate and will ensure the privacy, health, and welfare of research subjects during and after the study.

2.0 STUDY OBJECTIVES/AIMS AND ENDPOINTS

2.1 Primary objectives

- 2.1.1** To correlate quantitative metrics from imaging characterizing the tumor volume fraction associated with medium-to-high 18-FDG-PET uptake with the fraction of ccB-positive cores based on transcript analysis

2.3 Exploratory Objectives

2.3.1

2.3.2

3.0 PATIENT ELIGIBILITY

3.1 Inclusion Criteria

Subject must meet all of the inclusion criteria to participate in this study:

3.1.1 Age \geq 18 years of age (no upper age limit)

3.1.2 Has voluntarily provided signed informed consent to participate and HIPAA authorization for release of personal health information.

3.1.3 Must have clinically-suspected ccRCC based on prior imaging with tumor size \geq 4 cm.

3.1.4 Planned to have standard of care nephrectomy with a schedule that can accommodate a MR-FDG-PET scan within 4 weeks prior to surgery.

3.1.5 Must be able to understand and comply with study procedures for the entire length of the study.

3.1.6 Must receive their nephrectomy at UNC Chapel Hill Hospitals.

3.1.7 If patient has a history of prior malignancy, including melanoma, patient must be cancer-free for three or more years. Non-melanoma skin cancers will be included even if not cancer-free for three years.

3.1.8 Women of childbearing potential must have a negative urine pregnancy test performed the day of and prior to PET/MRI imaging.

3.1.9 Willing to undergo finger-stick blood glucose tests.

3.2 Exclusion Criteria

Any subject meeting any of the following exclusion criteria will be ineligible for study participation:

[figure not shown]
3.2.1 Inability to tolerate MRI (e.g., inability to lie flat for >1 hour or claustrophobia

requiring lorazepam to tolerate MRI),

- 3.2.2 Documented hypersensitivity to gadolinium contrast agent
- 3.2.3 Presence of pacemaker, intracranial aneurysm clip, bladder stimulator, cochlear implant or metal near eyes or near pelvis that would create excessive imaging artifact
- 3.2.4 Failure of two blood glucose tests (blood glucose level greater than 200 mg/dL) on day of first scheduled scan visit and on rescheduled day.
- 3.2.5 Patient receiving neoadjuvant therapy for RCC
- 3.2.6 Unwilling or unable to complete informed consent
- 3.2.7 Incarcerated patients or patients with medical power of attorney at time of enrollment

4.0 STUDY PLAN

4.1 Schema

¹ If glucose test is not passed ($>200\text{mg/dL}$) first time, subject can wait 30 minutes and repeat the test. If failed again, the subject can reschedule MRI and repeat glucose and pregnancy test. If failed twice on second try, the subject will be rescheduled for another day or excluded from the study.

² Subject will be given pre-MRI instructions. If both creatinine is $<1.8\text{mg/DL}$ and glucose test is $<200\text{mg/dL}$, then subject can undergo FDG and Gadolinium contrasting portions of protocol. If only glucose test is passed, then only the FDG imaging will be done.

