4.4 FDG-PET-MRI

All patients will undergo a MRI scan with simultaneous acquisition of [¹⁸F] Fludeoxyglucose Positron Emission Tomography (FDG F18- PET). 18F-FDG is a positron-emitting radiopharmaceutical used for diagnostic purposes. It is a glucose analog that concentrates in cells relying upon glucose as an energy source or in cells whose reliance on glucose increases under pathophysiological conditions. Each participant will receive approximately 12 mCi 18F-FDG, the exact dose administered to each participant will be measured and recorded in the study records

Subjects will have a finger-stick blood glucose test upon reporting to the imaging center; blood glucose must be below 200 mg/dL in order to proceed with the FDG injection. If blood glucose exceeds this level, a second finger-stick test may be performed after 30 minutes, and if the second test is below the threshold, the FDG injection may proceed. Failing the second test will result in the subject being rescheduled for another day or excluded from the study.

Injection of gadolinium contrast agent (if the serum creatinine test is passed: serum creatinine < 1.8 mg/dL) will be performed in the usual manner and images simultaneously obtained with MRI. If the serum creatinine is above the threshold, the subject will not receive gadolinium contrast, but the remainder of the scanning protocol will proceed.

Patients will have fasted for at least 6 hours before intravenous injection of FDG. To minimize radiation-absorbed dose to the bladder, patients should drink at least an 8 ounce glass of water prior to drug administration. Whenever possible, patients should take the following precautions for 12 hours after injection: used toilets should be flushed several times after each use, and hands should be washed thoroughly. If blood, urine or feces soil clothing, the clothing should be washed separately.

Each patient will be imaged at a single visit. Patients will be scheduled for PET-MRI imaging at Marsico Hall and will receive imaging-day instructions from the study coordinator. The study coordinator will meet the patient at the imaging facility and escort them to the imaging suite. Women of childbearing potential will undergo urine pregnancy test the day of and prior to the PET/MRI.

Patients will be paid \$50 each upon completion of the imaging visit as compensation for their time.

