7.0 STATISTICAL CONSIDERATIONS

7.1 Study Design/Study Endpoints

The purpose of the study is to assess the utility of combined, simultaneous positron emission tomography (PET) and magnetic resonance imaging (MRI), collectively called PET-MR, in predicting the fraction of tumor cores expressing the ccB subtype. The overall design is to image patients with PET-MR prior to surgery and evaluate quantitative metrics from imaging, and to evaluate the correlation of imaging metrics with the results of post-surgery transcriptome analysis. The primary endpoint is to correlate the MRI-guided PET metric fractional tumor volume over threshold SUV > 2.0 (FTVOT2) with the fraction of tumor cores classified as ccB from transcriptome analysis.

Patients will have suspected ccRCC based on imaging with tumor size ≥ 4 cm and for whom surgical treatment is planned. Once patient identification occurs, the patient will be assessed for the study via the inclusion and exclusion criteria mentioned above. The patient will then be approached by a study coordinator and

the study protocol explained and all risks outlined. If the patient provides informed consent the patient will be enrolled. Demographic data such as patient age, gender, comorbidities, and previous treatments, etc. will be collected. Tumor characteristics will be collected. All data collected will be kept on a password protected, secured server, and all physical documentation will be stored in a locked cabinet. All data will be collected by the PI, co-investigators and study coordinators.

Patients will then be scheduled for a pre-surgery PET-MR within four weeks of planned surgery.

For all PET scans, patients will be instructed to fast, and blood glucose level will be measured prior to injection of FDG; if blood glucose exceeds 200 mg/dL after two finger-stick tests, the patient will be rescheduled for another day or excluded from the study. Patients will be injected with approximately 12 mCi 18F-FDG, and then imaged starting 60 minutes post-injection for ten minutes each at one or two bed positions focused on the primary tumor site. MRI sequences to be run will include conventional anatomic T1- and T2-weighted sequences, high-resolution T1 pre- and post-contrast DCE sequences, and the PET-MR attenuation-correction sequence.

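### Does footnote 1 of section 4.1 undermine the trial by offering another scan day to a subject who already meets exclusion criterion 3.2.4?

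*Combined protocol and SAP*

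**What the plan says.** Footnote 1 of section 4.1 gives an ordered sequence. A subject above the glucose limit may repeat the test after half an hour. The next step is: "If failed again, the subject can reschedule MRI and repeat glucose and pregnancy test". The last is: "If failed twice on second try, the subject will be rescheduled for another day or excluded from the study".

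Exclusion criterion 3.2.4 reads: "Failure of two blood glucose tests (blood glucose level greater than 200 mg/dL) on day of first scheduled scan visit and on rescheduled day". The lead-in to section 3.2 leaves no discretion: "Any subject meeting any of the following exclusion criteria will be ineligible for study participation".

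Two other sections use nearly the same words as the end of the footnote. Section 4.4 says: "Failing the second test will result in the subject being rescheduled for another day or excluded from the study". Section 7.1 says that, for glucose above the limit "after two finger-stick tests, the patient will be rescheduled for another day or excluded from the study". Neither states whether it means the first visit or the rescheduled one.

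Section 4.2 removes from further participation anyone who does not meet the eligibility criteria. Section 8.5.2 rules out single-subject exceptions to eligibility.

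**The concern.** Two parts of one protocol appear to give different outcomes for the same subject. After failure on two separate days, 3.2.4 makes the subject ineligible, while the footnote keeps open a further appointment. Staff following the footnote could retain someone the eligibility section has ruled out, and section 8.5.2 provides no exception route. In a study planned for 17 eligible patients (section 7.2), even one disputed subject is noticeable. If the choice between rebooking and exclusion were left to staff and could be influenced by the study variables, there would also be a question about how the analysed sample was selected.

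**Working it through.** The plan states no figure on this point, so the check is a trace of the sequence followed by a look at what depends on it.

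**1. Trace of footnote 1 against 3.2.4.** The path allows two tests per visit, so two visits give 2 × 2 = 4 failed tests.

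| Visit | Failed tests, running count | Footnote 1 | Criterion 3.2.4 |
|---|---|---|---|
| First scheduled day | 1 and 2 | Rebook | Not met |
| Rescheduled day | 3 and 4 | Rebook or exclude | Met at test 3 if one failure per day is enough; at test 4 if two per day are needed |
| Third day, if offered | Tests 5 and 6 would fall here | Not described | Already met |

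On either count, 3.2.4 is met before a third day could begin. Only the rebooking branch conflicts with it.

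**2. Is there a reading without conflict?** The phrase *second try* might mean the same-day repeat, which would bring the footnote into line with 4.4 and 7.1. It fits poorly: the preceding sentence of the footnote already deals with that failure, and a single repeat test cannot be failed twice. The rescheduled day is the natural meaning.

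**3. One failure per day or two?** Section 4.4 allows a same-day repeat and lets the injection go ahead if the repeat passes. Counting one failure per day would rule a subject out at test 3, before that repeat. Two per day therefore fits the rest of the text better. The conflict in step 1 is the same on either count.

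**4. Do 4.4 and 7.1 add to the conflict?** No. Both can be read as rebooking after the first visit and exclusion after the second, which agrees with 3.2.4.

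**5. Does other text bear on the choice of branch?** Yes. Sections 3.2, 4.2 and 8.5.2 all treat a subject who meets an exclusion criterion as out of the study, without exceptions. The footnote itself lists exclusion as one of its two outcomes.

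**6. What depends on the choice statistically?**
- *Measurement.* Section 4.4 sets one condition for every injection: "blood glucose must be below 200 mg/dL in order to proceed with the FDG injection". Section 3.1.4 requires a nephrectomy "with a schedule that can accommodate a MR-FDG-PET scan within 4 weeks prior to surgery". A third-day scan would have to satisfy both, like any other scan.
- *Selection on the study variables.* The decision comes before FDG is injected, so FTVOT2 has not been measured. It also comes before surgery, so no cores have been classified. Neither variable of the Spearman correlation in section 7.3 can steer the choice.
- *Power.* Section 7.3 gives about 54% power at a correlation of 0.5 and 74% at 0.6, from N = 17 and a Type I error rate of 0.05. The glucose sequence does not enter that calculation, and section 7.2 defines the target as eligible patients.
- *Size.* One subject is 1/17 = 0.059, or about 5.9% of the planned sample. The documents do not give the chance of failing four tests over two days, so no expected number can be derived.

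**The case for a change.** The best case for a change is that the contradiction is plain, holds on either count of failures, and is cheap to remove. Section 8.5, on adherence, requires the study to be run exactly as written, which is impossible where two passages give different outcomes. A subject kept through the rebooking branch would be ineligible under 3.2.4, and a patient might be asked to attend a third time. A few words would settle it.

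Much of this stands. The wording conflict is real, and the footnote and 3.2.4 should be reconciled; which rule is intended is for the investigators. What does not follow is a defect in the statistical plan. The eligibility text already addresses the status of such a subject, and no bias, loss of power or altered conclusion can be shown under either branch. Cross-references in 4.4 and 7.1 are unnecessary, since those sections do not conflict with 3.2.4.

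**Conclusion.** No change to the plan follows. This is a clerical inconsistency: one branch of one footnote sentence is out of step with an exclusion criterion, and the other branch agrees with it. The primary correlation of FTVOT2 with the fraction of ccB cores, its test and its power statement are the same whichever branch staff follow. The most that can be said about size is 5.9% of the planned sample per affected subject, with the number affected unknown.

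The conclusion rests on two assumptions. The first is that *second try* means the rescheduled day; on the other reading, the conflict with 3.2.4 disappears and only clumsy wording remains. The second is that the schema drawing, which was not available in the text reviewed, does not set out a different sequence. The wording can be reconciled by the investigators as an editorial matter.
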